The particular assay is dependent on the mechanism of action of the agent being studied in MS. All are variations on the same limited theme; all require a modest amount of blood; and all are subject to the same confidentiality arrangements. As examples, we will use ELISA and RT-PCR to measure lymphocyte production of cytokines (such as IL-10 and IFN-gamma) protein and mRNA because of its relevance to immune function in MS patients before and after interferon therapy; use flow cytometry to measure lymphocyte B7.1 membrane expression for comparison to patients receiving Copaxone therapy, use Western blots and intracellular flow cytometry to measure STAT-1 levels for comparison to patients receiving interferon therapy, and use RT-PCR, micro arrays and next generation RNA sequencing to measure RNA levels and exon use.

Assays are done on blood from clinic population of MS patients and healthy agematched normal controls, and from clinical trial patients. Blood from patients who are not part of trials, and also from patients who are in trials--before and after drug therapy, will be analyzed during the course of the study and compared to untreated patients and controls Clinic visits typically occur at 3-12 month intervals. Trials of experimental or FDA-approved drugs last 1-3 years and typically require visits every 2-6 months. Blood will be drawn at regular clinic visits before therapy, at 1 & 3 mo, and at 1, 2, and 3 years after starting treatment, depending on duration of study. Research will take place in J218 and J220, SBRP.

Kinetics: Some patients with stable and active and progressive MS will be tested while on drug treatment. Here we will measure kinetic effects of immunomodulatory drugs. In the latter patients, blood will be drawn before, and at 4, 18, and 42 hours or 5 days after drug administration.

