DNA: Blood from some patients with each form of MS and family members will be analyzed for genes linked to MS and controlling immune function. In some cases, DNA may be obtained from buccal scraping or other body fluids. Multiple sclerosis is caused by interactions of multiple genes. This is a broad screen of multiple genes to determine linkage to MS, and to determine responses to interferons. Separate data on immune function, also without identifiers, will be compared to genes of interest. These genes include, but aren't limited to, those regulating all aspects of immunity, cell survival, matrix metalloproteases and migration, kinases and phosphatases, and cell cycling, and pH regulation.

In addition, we will assay methylation of DNA (circulating in plasma). Some genes are methylated, a marker of their ability to be turned on that reflects cell regulation and death. When cells die, they release DNA. Sensitive assays can detect methylated forms of DNA from relevant genes (*i.e.*, methylation-sensitive restriction enzyme digestion, then PCR).

Al of these assays are directed at finding the immunologic cause of MS, how to predict exacerbations, and how to optimize MS therapy.

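### Does holding the DNA and immune data without identifiers make the planned gene comparisons impossible?

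*Combined protocol and SAP*

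**What the plan says.** The document is a short combined protocol with no separate analysis section. Three statements in its DNA section matter here.

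- Who gives DNA: "Blood from some patients with each form of MS and family members will be analyzed for genes linked to MS and controlling immune function".
- What the screen is for: "This is a broad screen of multiple genes to determine linkage to MS, and to determine responses to interferons".
- How it relates to the laboratory data: "Separate data on immune function, also without identifiers, will be compared to genes of interest". The word 'also' implies that the DNA data are held without identifiers too.

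Two statements in the Immune function part of Study Design/Rationale bear on how records are kept. Of the assays it says that "all are subject to the same confidentiality arrangements", without describing those arrangements. On sampling it says "Blood will be drawn at regular clinic visits before therapy", then lists 1 and 3 months and 1, 2 and 3 years after treatment starts, depending on study duration. The Kinetics paragraph adds samples before a drug dose and at 4, 18 and 42 hours or 5 days after it.

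No section mentions a subject code, a family code, a key or a joining procedure. No section says that samples are irreversibly anonymised.

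**The concern.** Relating genotype to immune function, or to interferon response, requires each person's genotype to sit beside that person's own assay values and treatment record. Using family members to study linkage requires knowing which samples belong to one family, how the donors are related and who is affected.

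If both files were stripped of every link, neither requirement could be met. Only group summaries could be set side by side, and relatives might be analysed as unrelated people. A larger sample would not help, because the missing item is the pairing and not precision. Anonymising at collection also could not be undone later. That would put at risk the comparison with immune data and, unless response was recorded with the DNA sample, the interferon-response aim.

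**Working it through.** The plan states no sample size, power or error rate that depends on record linkage, so there is no figure to reproduce. The check is mainly one of reading.

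**1. Is the conditional claim right?** Yes. If genotype and assay values are paired at random, they are independent by construction and their expected correlation is zero, whatever the true association and whatever the number of people. A simulation of this only restates the premise and carries no information about this study.

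**2. Do the documents establish the condition?** Set side by side:

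| Text | What it implies about linkage |
|---|---|
| Data are separate and without identifiers (DNA) | Compatible with full anonymisation, and equally with coded records held in separate files |
| The two are to be compared (DNA) | Presupposes some way of joining them |
| Interferon response is an aim of the gene screen (DNA) | Presupposes that genotype is tied to treatment or response status |
| Draws before therapy and at five times after (Immune function) | 1 + 5 = 6 scheduled draws at most per patient, which presupposes tracking of the person |
| Draws before and after a dose (Kinetics) | Within-person tracking over hours or days |
| Shared confidentiality arrangements (Immune function) | A scheme exists but is not described here |

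Only the first row can be read as ruling out a link, and it has an ordinary reading that does not. The others lean towards coded records or are silent.

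**3. Does losing identifiers remove everything useful?** No. A DNA record can carry affected status, treatment, responder status and relationship to another donor without naming anyone. Affected-versus-unaffected and responder-versus-non-responder comparisons would survive. Only the join to separately held assay values needs a common code.

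**4. Would relatives make the standard errors too small?** The plan names no analysis model and no family-based method, so any answer concerns an analysis it does not state. The direction also depends on the contrast. Assume, for illustration, sibling pairs with genotype correlation ρ = 0.5, no association with disease, and genotype variance σ².

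- Both siblings in the same group: the variance of the pair mean is σ²(1 + ρ)/2 = 0.75σ², against a naive 0.5σ². The naive standard error is √(0.5/0.75) ≈ 0.82 of the true one, which is too small.
- Patient against own unaffected sibling: the variance of the difference is 2σ²(1 − ρ) = σ², against a naive 2σ². The naive standard error is √2 ≈ 1.41 times the true one, which is too large.

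A general statement that error bars would be too narrow is therefore not supported.

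**The case for a change.** The strongest reply is that serial sampling shows at most that the immune data are tracked within person. It does not show that the DNA file carries the same code, and it says nothing about families. The one sentence that addresses the join calls the data separate and without identifiers. A laboratory following it literally could break the link permanently, whereas one clarifying sentence would cost almost nothing.

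Part of this stands. The document does not describe the code, and the serial sampling is indirect evidence as far as the DNA file is concerned. If samples really were anonymised beyond recovery, the per-person comparison with immune data would be lost.

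The step from an undescribed code to an absent one does not stand. The sentence in question announces the comparison, so reading it as forbidding the join sets it against its own purpose. The confidentiality arrangements are mentioned but not visible, and the consent pages are not in this copy, so absence cannot be inferred. The family part is weaker still. "Blood from some patients with each form of MS and family members will be analyzed for genes linked to MS" says who is sampled, the linkage aim attaches only to the DNA screen, and a pedigree method is inferred from the word linkage, not stated.

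**Conclusion.** No change to the plan follows. The text leaves a gap in description: it does not say whether the records are coded or how the DNA, immune and family records are joined. Investigators who mean to carry out the comparison they announce would fill that gap sensibly, with a study code kept apart from names and a note of who is related to whom. The size of the effect on the plan's own figures is nil, because none depends on it.

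This rests on two assumptions. One is that being without identifiers has its ordinary meaning, that direct personal identifiers are removed. The other is that the undescribed confidentiality arrangements do not require links to be destroyed. If the second were false, the per-person genotype–immune comparison could not be made. Nothing in the documents indicates that it is false.
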